## 6. 6-Week Visit with Study Physician

### *Prior to Visit*

- a. Dose adjustment may be required before this visit, particularly if there are reports of severe adverse events (e.g. unremitting GI issues) or lack of efficacy. When this occurs, the study physician may adjust the ATX regimen as needed. Documentation of changes will be recorded in the participants electronic medical record. If a new prescription is required, the study physician will follow the procedures outlined in “Other visit related activities,” (see below).
- b. Send out the following psychometric questionnaires 1-2 weeks prior to 6-Week Visit with Study Physician:
  - i. Medication Side Effects (parent and teacher informant)
  - ii. NICHQ Vanderbilt Assessment Scales follow-up assessment (parent and teacher informant)
  - iii. Please note: Responses will always be sought, but the study team recognizes the potential difficulties with returning results, particularly during the summer break or the pandemic for teachers. The study team will remind the parent to complete his or her questionnaires a maximum of 3 times if applicable to the participant’s school situation. Additionally, the study team will encourage parents to reach out to their child’s teacher(s) to return questionnaires as well. A reminder for parents to reach out to teachers will occur a maximum of 3 times.
  - iv. Questionnaires should be returned  $\pm$  2 weeks of study visit with physician.
  - v. If questionnaires are late or are not received, this will be noted on CRFs and are considered “missing data.”
  - vi. Both the Medication Side Effects and NICHQ Vanderbilt Assessment scales are validated questionnaires that are used to aid Study Physician in determining treatment response. Use of different versions of these questionnaires are permissible to aid the Study Physician, in addition to clinical impression, with medication management and determination of response.
- c. Contact participant and participant’s family 1 -2 days prior to 6-Week Visit with Study Physician to:
  - i. Remind them of their scheduled 6-Week Visit with Study Physician.
  - ii. Remind participant to bring their home atomoxetine medication to 6-Week Visit with Study Physician (in-person visit only).

- iii.* Remind participant to bring U54 Study Booklet, which contains the participant's medication calendar (in-person visit only).

*Day of Visit*

- a.* This visit may occur in-person or via telehealth, at the Study Physician's discretion.
      - b.* If this visit occurs in-person:
        - i.* The research team will ensure that the participant and their family are aware of the safety measures at Children's Mercy Hospital to prevent transmission of the SARS-CoV-2 virus. These resources and information to be shared will be detailed on the Children's Mercy Hospital homepage.
        - ii.* Conduct physical exam. Documentation will be in EMR.
        - iii.* Assess ADHD symptoms/review questionnaires.
        - iv.* Assess other comorbidities and concurrent medications. Add to Concomitant and Prior Medications Log.
        - v.* Assess for atomoxetine side effects.
        - vi.* Make atomoxetine dose changes as necessary, with guidance from study team if necessary and document reason for changes.
        - vii.* Document prescription change (if made) in CRF.
        - viii.* Assess for adverse events. Document in Adverse Events log.
        - ix.* Verify medication calendar with remaining capsules count.
        - x.* Make copies of pages in medication calendar.
        - xi.* Complete Clinical Global Impression (CGI)
    - c.* If this visit occurs via telehealth proceed with all procedures stated above with the following exceptions:
      - i.* The physical exam will be omitted.
      - ii.* Ask the participant to email pictures of the pertinent adherence calendar pages and a picture of the remaining medication.

*Other Visit Related Activities*

- a.* Obtain a signed and dated prescription for atomoxetine from Study Physician. This may occur prior, during, or after this visit.
      - b.* Submit signed and dated prescription to Children's Mercy Hospital Investigation Drug Services (IDS) pharmacy.
      - c.* Deliver medication to patient, or leave medication at Children's Mercy Outpatient Pharmacy for family to pick up medication at their convenience. Medication may be mailed (see section 5.2) at the request of the participant's family.

- d. Add compensation to participant's Greenphire account if calendar and medication bottle brought to visit.
  - e. If Children's Mercy Hospital develops procedures for drive-up collection of vital signs (e.g. heart rate, blood pressure), the Study Physician may ask the participant to use this service to supplement their evaluation.

## 7. 12-Week Visit with Study Physician

### *Prior to Visit*

- a. Dose adjustment may be required before this visit, particularly if there are reports of severe adverse events (e.g. unremitting GI issues) or lack of efficacy. When this occurs, the study physician may adjust the ATX regimen as needed. Documentation of changes will be recorded in the participants electronic medical record. If a new prescription is required, the study physician will follow the procedures outlined in "Other visit related activities," (see below).
  - b. Send out the following psychometric questionnaires 1-2 weeks prior to 12-Week Visit with Study Physician:
    - i. Medication Side Effects (parent and teacher informant)
    - ii. NICHQ Vanderbilt Assessment Scales follow-up assessment (parent and teacher informant)
    - iii. Please note: Responses will always be sought, but the study team recognizes the potential difficulties with returning results, particularly during the summer break or the pandemic for teachers. The study team will remind the parent to complete his or her questionnaires a maximum of 3 times if applicable to the participant's school situation. Additionally, the study team will encourage parents to reach out to their child's teacher(s) to return questionnaires as well. A reminder for parents to reach out to teachers will occur a maximum of 3 times.
    - iv. Questionnaires should be returned  $\pm$  2 weeks of study visit with physician.
    - v. If questionnaires are late or are not received, this will be noted on CRFs and are considered "missing data."
    - vi. Both the Medication Side Effects and NICHQ Vanderbilt Assessment scales are validated questionnaires that are used to aid Study Physician in determining treatment response. Use of different versions of these questionnaires are permissible to aid the Study Physician, in addition to clinical impression, with medication management and determination of response.

- c. Contact participant and participant's family 1 -2 days prior to 12-Week Visit with Study Physician to:
  - i. Remind them of their scheduled 12-Week Visit with Study Physician.
  - ii. Remind participant to bring their home atomoxetine medication to 12-Week Visit with Study Physician (in-person visit only).
  - iii. Remind participant to bring U54 Study Booklet, which contains the participant's medication calendar (in-person visit only).

*Day of Visit*

- a. This visit may occur in-person or via telehealth, at the Study Physician's discretion.
- b. If this visit occurs in-person:
  - i. Conduct physical exam. Documentation will be in EMR.
  - ii. Assess ADHD symptoms/review questionnaires.
  - iii. Assess other comorbidities and concurrent medications. Add to Concomitant and Prior Medications Log.
  - iv. Assess for atomoxetine side effects.
  - v. Make atomoxetine dose changes as necessary, with guidance from study team if necessary and document reason for changes.
  - vi. Document prescription change (if made) in CRF.
  - vii. Assess for adverse events. Document in Adverse Events log.
  - viii. Verify medication calendar with remaining capsules count.
  - ix. Make copies of pages in medication calendar.
  - x. Complete Clinical Global Impression (CGI)
- c. If this visit occurs via telehealth, proceed with all procedures stated above with the following exceptions:
  - i. The physical exam will be omitted.
  - ii. Ask the participant to email pictures of the pertinent adherence calendar pages and a picture of the remaining medication.

*Other Visit Related Activities*

- a. Obtain a signed and dated prescription for atomoxetine from Study Physician. This may occur prior, during, or after this visit.
- b. Submit signed and dated prescription to Children's Mercy Hospital Investigation Drug Services (IDS) pharmacy.
- c. Deliver medication to patient, or leave medication at Children's Mercy Outpatient Pharmacy for family to pick up medication at

their convenience. Medication may be mailed (see section 5.2) at the request of the participant's family.

Add compensation to participant's Greenphire account if calendar and medication bottle brought to visit.

d. If Children's Mercy Hospital develops procedures for drive-up collection of vital signs (e.g. heart rate, blood pressure), the Study Physician may ask the participant to use this service to supplement their evaluation.

## 8. 18-Week Visit with Study Physician

### *Prior to Visit*

- a. Dose adjustment may be required before this visit, particularly if there are reports of severe adverse events (e.g. unremitting GI issues) or lack of efficacy. When this occurs, the study physician may adjust the ATX regimen as needed. Documentation of changes will be recorded in the participants electronic medical record. If a new prescription is required, the study physician will follow the procedures outlined in “Other visit related activities,” (see below).
- b. Send out the following psychometric questionnaires 1-2 weeks prior to 18-Week Visit with Study Physician:
  - i. Medication Side Effects (parent and teacher informant)
  - ii. NICHQ Vanderbilt Assessment Scales follow-up assessment (parent and teacher)
  - iii. Strengths and Difficulties Questionnaire (parent and teacher informant)
  - iv. Child Behavior Checklist (parent and teacher informant)
  - v. School Intervention Questionnaire (teacher informant)
  - vi. Please note: Responses will always be sought, but the study team recognizes the potential difficulties with returning results, particularly during the summer break or the pandemic for teachers. The study team will remind the parent to complete his or her questionnaires a maximum of 3 times if applicable to the participant’s school situation. Additionally, the study team will encourage parents to reach out to their child’s teacher(s) to return questionnaires as well. A reminder for parents to reach out to teachers will occur a maximum of 3 times.
  - vii. Questionnaires should be returned ± 2 weeks of study visit with physician.

- viii. If questionnaires are late or are not received, this will be noted on CRFs and are considered “missing data.”
- vii. All clinical questionnaires are validated tools that are used to aid the Study Physician in determining treatment response. Use of different versions of these questionnaires are permissible to aid the Study Physician, in addition to clinical impression, with medication management and determination of response.

b. Contact participant and participant’s family 1 -2 days prior to 18-Week Visit with Study Physician to:

- i. Remind them of their scheduled 18-Week Visit with Study Physician.
- ii. Remind participant to bring their home atomoxetine medication to 18-Week Visit with Study Physician (in-person visit only).
- iii. Remind participant to bring U54 Study Booklet, which contains the participant’s medication calendar (in-person visit only).

*Day of Visit*

- a. This visit may occur in-person or via telehealth, at the Study Physician’s discretion.
- b. If this visit occurs in-person:
  - i. Conduct physical exam. Documentation will be in EMR.
  - ii. Assess ADHD symptoms/review questionnaires.
  - iii. Assess other comorbidities and concurrent medications. Add to Concomitant and Prior Medications Log.
  - iv. Assess for atomoxetine side effects.
  - v. Make atomoxetine dose changes as necessary, with guidance from study team if necessary and document reason for changes.
  - vi. Document prescription change (if made) in CRF.
  - vii. Assess for adverse events. Document in Adverse Events log.
  - viii. Verify medication calendar with remaining capsules count.
  - ix. Make copies of pages in medication calendar.
  - x. Complete Clinical Global Impression (CGI)
- c. If this visit occurs via telehealth, proceed with all procedures stated above with the following exceptions:
  - i. The physical exam will be omitted.

- ii.* Ask the participant to email pictures of the pertinent adherence calendar pages and a picture of the remaining medication.

*Other Visit Related Activities*

- a.* Obtain a signed and dated prescription for atomoxetine from Study Physician. This may occur prior, during, or after this visit.
      - b.* Submit signed and dated prescription to Children's Mercy Hospital Investigation Drug Services (IDS) pharmacy.
      - c.* Deliver medication to patient, or leave medication at Children's Mercy Outpatient Pharmacy for family to pick up medication at their convenience. Medication may be mailed (see section 5.2) at the request of the participant's family.
      - d.* Add compensation to participant's Greenphire account if calendar and medication bottle brought to visit.
      - e.* If Children's Mercy Hospital develops procedures for drive-up collection of vital signs (e.g. heart rate, blood pressure), the Study Physician may ask the participant to use this service to supplement their evaluation.

## **9. Research Visit 4**

*Prior to Visit*

- a.* Optional: Obtain a signed and dated prescription by a Study Physician for topical lidocaine (either J-tip or cream) to alleviate pain with needlestick for participant.
        - b.* Submit signed and dated prescription to Children's Mercy Hospital Investigation Drug Services (IDS) pharmacy.
        - c.* Confirm participation in Study Design 1, Study Design 2, or need to switch to Study Design 3.
        - d.* If participant will be changing to Study Design 3 or back to Study Design 2, discuss with participant and/or family changes from prior study design.
        - e.* Contact participant and participant's family 8-10 days prior to Research Visit 4 to remind participant to take all prescribed doses of medication in the week prior to Research Visit 4.
        - f.* If participant has been switched to evening dosing of ATX, schedule Research Visit 4 to mirror how the participant typically takes their medication (i.e. if the participant takes their medication in the evening, the beginning of their pharmacokinetic study should also be in the evening).
        - g.* Contact participant and participant's family 1 -2 days prior to Research Visit 4 to:
          - i.* Remind them of their scheduled visit.

- ii. Ensure that participant has been compliant on medication for 1 week prior to scheduled Research Visit 3.
  - i. If the participant has not been compliant, the visit will need to rescheduled.
- iii. Instruct participant to begin fasting at midnight prior to visit. Water is permissible while fasting.
- iv. Remind participant to bring their home atomoxetine medication to the PCRU, but to not take the medication in the morning.
- v. Remind participant to bring U54 Study Booklet, which contains the participant's medication calendar.
- vi. The research team will ensure that the participant and their family are aware of the safety measures at the Children's Mercy Hospital to prevent transmission of the SARS-CoV-2 virus. These resources and information to be shared will be detailed on the Children's Mercy Hospital homepage and any PCRU guidance in response to COVID-19.

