### Secondary Objective(s):

- To establish the relationship between ATX systemic exposure, inhibition of the norepinephrine uptake transporter, and therapeutic response
- To determine global baseline patient characteristics differences between ATX responders and non-responders.
- To explore how baseline oral microbiome make-up influences clinical outcomes and to describe changes in the oral microbiome with ATX therapy.
- To refine the iGO-PK ATX dosing algorithm.
- To evaluate comprehension of the study procedures by study participants and their families when an illustrated study booklet is supplied with a consent form (please see Supplementary Documents, “U54 Study Booklet” and “U54 Study Booklet Information Handout”).
- To validate a urinary CYP2D6 phenotype biomarker.

[figure not shown]

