The *CYP2D6* gene, which encodes for the drug metabolizing enzyme CYP2D6 responsible for the clearance of ATX from the body, is highly polymorphic (Gaedigk et al., 2007; Gaedigk et al., 2010; Gaedigk et al., 2010; Gaedigk, 2013). ATX metabolism by CYP2D6 protein is one of the major routes of clearance (i.e., removal) of this drug. Genetic variability in the *CYP2D6* gene leads to wide inter-individual variability in the activity of the enzyme, ultimately resulting in differing amount of drug in the body (also referred to as “exposure,” and is a component of drug pharmacokinetics). Secondly, the *SLC6A2* gene which encodes for the norepinephrine reuptake transporter, the drug target for ATX, is also subject to genetic variation. Reported genetic variants of *SLC6A2* have been associated with decreased abundance of the transporter (Kim et al., 2006). The consequences of *SLC6A2* genetic variation with regards to ATX clinical response are currently unknown. In the context of distinct “responder” and “non-responder” groups with a population of atomoxetine-treated patients, non-response could be due to definable differences at the level of the drug target (patients unlikely to respond regardless of the ATX concentrations achieved), or simply a consequence of inadequate exposure in a substantial proportion of population. The goal of this study is to address this issue.

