18-Week Visit with Study Physician – The participant and family meet with a study physician approximately 6 weeks after the 12-Week Visit with Study Physician. A ± 2-week window is allowed for ease of scheduling. Prior to this visit, questionnaires will be sent out via CHADIS to parents and teachers to assess participant's behavior. During this visit, safety, efficacy, and side effects will be assessed and dose adjustments will be made accordingly. In addition, baseline questionnaires will be re-administered to gauge symptom and impairment changes post-treatment initiation. Dose adjustments may be outside research and visits with study physicians as needed.

Research Visit 4 – This visit is also referred to as pharmacokinetic study 3 (PK3) or end of study PK. This vist occurs after the 18-Week Visit with Study Physician. This visit takes place in the PCRU and consists of the same procedures as Research Visit 3. Determination of Study Design will be confirmed prior to visit, as some participants may require switching to a different study design if frequency of dosing has changed. During this visit, baseline psychometric measures will be re-administered to measure change post-treatment initiation. An end of study EKG will be obtained, and a Dietary Survey Questionnaire will be administered.

- Description of Research Procedures

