### *Prior to Visit*

- a. Optional: Obtain a signed and dated prescription from a Study Physician for topical lidocaine (either J-tip or cream) to alleviate pain with needlestick for participant.
- b. Submit signed and dated prescription to Children's Mercy Hospital Investigation Drug Services (IDS) pharmacy.
- c. Confirm participation in Study Design 1, Study Design 2, or need to switch to Study Design 3.
- d. If participant will be changing to Study Design 3, discuss with participant and/or family changes from Study Design 2.

- e. Contact participant and participant's family between 8-10 days prior to Research Visit 3 to remind participant to take all prescribed doses the week prior to Research Visit 3.
- f. Contact participant and participant's family 1 -2 days prior to the visit to:
  - i. Remind them of their scheduled visit.
  - ii. Ensure that participant has been compliant on medication for 1 week prior to scheduled Research Visit 3.
    - i. If the participant has not been compliant, the visit will need to rescheduled.
  - iii. Instruct participant to begin fasting at midnight prior to the visit. Water is permissible while fasting.
  - iv. Remind participant to bring their home atomoxetine medication to the PCRU, but to not take the medication in the morning.
  - v. Remind participant to bring U54 Study Booklet, which contains the participant's medication calendar.
  - vi. If participant has been switched to evening dosing of ATX, schedule Research Visit 3 to mirror how the participant typically takes their medication. (i.e. if the participant takes their medication in the evening, the beginning of their pharmacokinetic study should also be in the evening).
  - vii. The research team will ensure that the participant and their family are aware of the safety measures at Children's Mercy Hospital to prevent transmission of the SARS-CoV-2 virus. These resources and information to be shared will be detailed on the Children's Mercy Hospital homepage and any PCRU guidance in response to COVID-19.

*On Day of Visit*

- a. Confirm participant's willingness to continue in the research study.
- b. Obtain medication history and concomitant medications. Add to Concomitant and Prior Medications Log.
- c. Verify medication calendar with remaining capsules count.
- d. Make copies of pages in medication calendar.
- e. Measure vital signs: height, weight, blood pressure, heart rate, respiration rate, and temperature.
- f. Perform physical exam.

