### *On Day of Visit*

- a. Confirm participant's willingness to continue in the research study.
- b. Obtain medication history and concomitant medications. Add to Concomitant and Prior Medications Log.
- c. Verify medication calendar with number of remaining capsules.
- d. Take back medication calendar.
- e. Measure vital signs: height, weight, blood pressure, heart rate, respiration rate, and temperature.
- f. Perform physical exam.
- g. Place indwelling venous catheter to obtain blood samples for safety labs and for atomoxetine pharmacokinetic and pharmacodynamic analysis.
- h. Collect blood samples for the following safety laboratory tests (to be processed immediately at Children's Mercy Hospital): CBC with differential, basic metabolic panel, and liver function test. These tests may be omitted if these data were collected in the week prior, at the discretion of the study coordinator, the physician performing the physical exam or any person designated in the delegation of authority log.
- i. Collect urine for urinalysis with microbiology.
- j. Perform urinary pregnancy test on female subjects 10 years of age or older.

- k. Collect baseline urine sample (~10 mL) for predose urine sample and CYP2D6 biomarker analysis.
- l. Confirm prior to dosing that participant is:
  - i. Healthy enough to continue Research Visit 4 (sign off on safety labs and physical exam sheet by physician).
  - ii. Not pregnant, females only (urine pregnancy test).
  - iii. Has been compliant with medication (medication calendar check). If the participant has not been compliant, the visit will need to rescheduled.
- m. Place two sweat patches on the participant's back. The sweat patch is 15.4 cm^2 in size and consists of a cellulose blotter paper collection pad (PharmChek®, PharmaChem Laboratories, Menlo Park, CA). Prior to patch placement, clean the area of skin to which the patch will be applied with rubbing alcohol.
- n. Collect pre-dose blood, blood pressure, and heart rate prior to dosing medication.
- o. Administer dose of atomoxetine according to prescription.
- p. Collect 3 mL of blood, blood pressure, and heart rate at the following time points after dose administration:
  - i. Timeframe:
    - i. Study Design 1: 0.5, 0.75, 1, 1.5, 2, 3, 4, 6, 8, 10, 12, 16, 20, and 24 hours.
    - ii. Study Design 2: 0.5, 0.75, 1, 1.5, 2, 3, 4, 6, 8, 10, and 12 hours.
    - iii. Study Design 3:

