#### Pupillometry Analysis:

Changes in performance during Posner Cuing Task will be measured as a function ATX exposure and  $C_{max}$  concentrations. Pupil size will be measured during two types of activities: localization and discrimination tasks. Pupil size differences during localization tasks report on the individuals' baseline (tonic) release of norepinephrine. This corresponds to endogenous, or volitional attention. Pupil size differences during discrimination tasks is a composite of the individuals' baseline (tonic) and situational (phasic) release of norepinephrine. Currently it is unclear whether tonic, phasic, or both are impaired in individuals with ADHD.

Cardiovascular Marker Analysis:

Changes in heart rate will also be measured as a function ATX exposure and  $C_{max}$  concentrations. One side effect of ATX that is directly related to the pharmacodynamics of the drug is an increased heart rate due to increased concentration of norepinephrine in blood. We would like to understand the extent of this side effect as a function of increased systemic ATX exposure and  $C_{max}$ . By studying these two components, we will be able to distinguish ATX drug action in central and peripheral nervous systems.

Pharmacodynamic Changes Correlated with change in NICHQ Vanderbilt Assessment Scales:

All changes markers of pharmacodynamic action will be correlated with whether a child is classified as a responder or non-responder; and tolerant or intolerant (see Clinical Outcomes below for details). Extent of adherence will be used as a confounding factor in both of these analyses.

Clinical Outcomes:

Determine and document participant response to ATX therapy:

- Responders will be defined as:
  - Participants, who after approximately 18 weeks of continuous treatment with ATX, demonstrate  $\geq 40\%$  reduction of baseline ADHD symptom score;
  - OR the Clinical Global Improvement rating is 1 or 2 (Very Much Improved or Much Improved).
- Non-responders will be defined as:
  - Participants, who after approximately 18 weeks of continuous treatment with ATX, demonstrate  $< 40\%$  reduction of baseline ADHD symptom score, AND the Clinical Global Improvement score  $\geq 3$ .
  - Participants who discontinue ATX prior to the planned end of study (18 weeks) due to perceived lack of efficacy despite dose escalation.

Determine and document participant tolerance of ATX therapy:

- ATX intolerant participants are:

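### Exposure and drug-effect markers at RV3 and RV4 follow a prompted, checked week of dosing, but the 18-week response rating has no adherence condition and measured exposure is not corrected for missed doses

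*Combined protocol and SAP*

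**What the plan says.** Section 11.2 conditions both steady-state visits on adherence. Families are called 8-10 days ahead, for RV3 to "remind participant to take all prescribed doses the week prior to Research Visit 3" and for RV4 to "remind participant to take all prescribed doses of medication in the week prior to Research Visit 4". A second call comes 1-2 days ahead. On the day, before dosing, staff confirm that the child "Has been compliant with medication (medication calendar check). If the participant has not been compliant, the visit will need to rescheduled". No threshold for compliance is given. (The second RV4 call refers to compliance before Research Visit 3, apparently a carry-over to be reconciled.)

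Response is defined in section 20.1 from the symptom score and the Clinical Global Impression (CGI) at about 18 weeks, using parent questionnaires. Questionnaires count if returned within 2 weeks either side of the 18-week visit, and the CGI is completed at that visit. Neither has an adherence condition beyond an undefined reference to continuous treatment. On RV4, section 11.1 says: "This vist occurs after the 18-Week Visit with Study Physician". The Schedule of Events gives RV4 no window.

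On adherence, capsules are counted against the calendar at RV3, at the 6-, 12- and 18-week visits and at RV4. At RV4 adherence is classed as high (at least 80% of doses), medium (40-79%) or low (below 40%). For the analyses relating pharmacodynamic markers to response and tolerance, section 20.1 says: "Extent of adherence will be used as a confounding factor in both of these analyses".

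**The concern.** Section 3.1 sets the study's question: "non-response could be due to definable differences at the level of the drug target", or it could reflect inadequate exposure. Missed doses are one form of inadequate exposure. RV4 is poorly placed to show it, because the visit is postponed until the child has been compliant. Its concentrations, plasma DHPG and pupil measures describe a prompted week, whereas the 18-week rating describes whatever was taken before it.

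A secondary objective is "To establish the relationship between ATX systemic exposure, inhibition of the norepinephrine uptake transporter, and therapeutic response". No adherence correction is planned for the exposure term in that analysis. A child who fails to respond because doses were missed can appear in it with higher exposure than he or she had when rated, and so look like a target-level non-responder. The dose may also be changed at the 18-week visit, so RV4 can be run on a different dose from the one that was rated.

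**Working it through.** **1. How far RV4 exposure can overstate rated-period exposure.** Assume linear kinetics, so that average exposure is proportional to doses taken. Then overstatement = 1 / fraction taken.
- High class: 1/0.80 = 1.25 at most.
- Medium class: 1/0.79 = 1.27 to 1/0.40 = 2.5.
- Low class: above 2.5.

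The medium class alone spans 0.79/0.40 = 1.98-fold, about as wide as the whole target range in section 5.1 (800/400 = 2). For example, a child taking 45% of a regimen aimed at 800 ng/mL averages the equivalent of 0.45 x 800 = 360 ng/mL. A three-class covariate leaves most of that spread uncorrected.

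**2. The plan's own detectable difference.** Inputs from section 20.2: 30% responders, one-sided alpha 0.05, 80% power. With 120 children (36 versus 84), the normal approximation is (1.645 + 0.842) x sqrt(1/36 + 1/84) = 0.495 SD. The noncentral t gives 0.498 SD, and power at 0.5 SD is 80.3%, so the stated 0.5 SD reproduces. With 96 children (29 versus 67) it is 0.557 SD, which matches the stated 0.6 after rounding.

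**3. Effect on a two-sample marker contrast.** The two-sample and proportions tests named in sections 20.1 and 20.2 carry no adherence term. Assume that a share f of recorded non-responders are poor adherers with responder-like markers. The documents give no f. With true difference d, the observed difference is d(1-f) and the non-responder variance is 1 + f(1-f)d². For 120 children, d = 0.5 and f = 0.20:
- difference 0.5 x 0.8 = 0.40
- variance 1 + 0.2 x 0.8 x 0.25 = 1.04
- pooled SD 1.014, standardised difference 0.394, power 63%.

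| f | Power, no adherence handling | Power, poor adherers set aside |
|---|---|---|
| 0 | 80% | 80% |
| 10% | 72% | 79% |
| 20% | 63% | 78% |
| 30% | 53% | 76% |

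**4. Illustrative simulation of misattribution.** All inputs are assumed except the 400/600/800 ng/mL targets:
- 10-40% of children take 40-80% of doses and the rest 80-100%
- exposure varies by 35% around target
- the target is raised on non-response
- each child has a response threshold (log-normal, median 700 ng/mL, log SD 0.6).

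A misattributed non-responder is one who would have responded at the recorded exposure.

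| Share of children below 80% | Misattributed, as % of non-responders | Of these, below 80% | Of these, 80-100% |
|---|---|---|---|
| 0 | about 13% | 0 | about 13% |
| 10% | 17% | 6% | 11% |
| 40% | 26% | 20% | 6% |

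The simulated response rate for the last two rows is 43-49%, above the plan's 30%.

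**The case against.** The plan does not ignore adherence. It counts capsules at every visit, classes adherence, analyses it as an outcome and names it as a confounder. Section 16.1 also allows withdrawal for non-compliance. This stands, and it means that a poor adherer is recorded with an adherence class and not simply as a non-responder at full exposure. However, the confounder sentence covers the marker-response and tolerance analyses, not the exposure-response objective, and it gives no interval, coding or model. The withdrawal ground has no threshold, and a class below 40% is defined at RV4, so such children may well remain.

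Prompted and rated weeks can overlap. RV4 has no minimum gap after the 18-week visit, questionnaires are accepted up to 2 weeks after that visit, and RV3 may fall at any time up to it. This stands too, but nothing ensures the overlap.

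Many measurements are unaffected: RV2 markers after an observed dose, baseline DHPG, genotype, and IC50 and Imax fitted to concurrent concentrations.

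A reader might infer that the mismatch reverses the exposure-response relation, because recorded exposure in the simulation is 4-5% higher in non-responders. The documents do not support that reading. The excess comes from raising the target on non-response: it is about 6-8% with every child at 100% adherence. Without escalation, recorded exposure is 27% lower in non-responders even with 40% poor adherers. Nor do the documents show that poor adherers have full DHPG suppression at RV4.

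**Conclusion.** The mismatch is in the text and bears on the study's central distinction. For children who miss doses, RV4 exposure can overstate exposure in the rated weeks, and the adherence adjustment that would deal with this is named but not specified. Misclassification is possible, not automatic. It requires missed doses that actually lower response.

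The exposure overstatement rests only on proportionality to doses taken. The power loss at 120 children (from 80% to 72-53% for f of 10-30%) rests on an assumed f. The simulated 17-26% should not be read as the effect of poor adherence: it depends on assumed thresholds, and about 13% appears with no child below 80%. The part attributable to children below 80% adherence is about 6-20% of labelled non-responders. This is a worthwhile and inexpensive improvement to the analysis plan, not a demonstrated bias in its results.

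**What to change.** Keep the compliance rule for the pharmacokinetic visits. In section 20.1:

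- For the exposure-response analysis, use average exposure over the rated interval: daily dose prescribed in that interval x fraction of capsules taken between the 12- and 18-week visits / CL/F. Report it beside RV4 Cmax,ss.
- Compute steady-state CL/F as dose / AUC over the dosing interval, or use the single-dose CL/F from RV2. The steady-state table in 20.1 divides by AUC to infinity, which at steady state understates clearance and would inflate the new exposure measure.
- The exposure term does not correct DHPG or pupil measures. For those contrasts, enter adherence over the same interval as a continuous covariate, and repeat the responder versus non-responder comparisons in children who took at least 80% of doses.

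The cost is some SAP wording and modest analysis, since the capsule counts are already collected. The repeat analysis has somewhat fewer children, and counts at telehealth visits rely on emailed photographs.
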